# 7.6 Enrollment

Patients are considered to be enrolled after all Pre- and Intra-Procedure Inclusion Criteria and none of the Pre- and Intra-Procedure Exclusion Criteria are met and beginning of Luxabite material or Tooth Cap. Once patients are enrolled in the study, they are considered subjects.

# 7.6.1 Screen Failures

Patients that were consented but that did not meet all Pre- and Intra-Procedure Inclusion Criteria and/or met any Pre- and Intra-Procedure Exclusion Criteria are considered Screen Failures. Screen Failures will be treated and followed according to standard of care by their Screening Dentist or endodontist, but will not be documented or followed for study purposes.

A Screen Failure patient will be counseled by the endodontist on any treatment they require. The patient will be responsible for any standard of care treatments.

# 7.6.2 Subject Identification

Once a subject is enrolled in the study, they will be assigned a Subject Identification (ID) code. A Subject ID is a numeric six (6) digit code: XXX-XXX. The first set of three (3) numbers is the clinical site number. The second set of three (3) numbers is a sequential number starting at 001; each

clinical site will start at 001. Therefore, the first subject enrolled at site 101 is 101-001, the second is 101-002, and so forth.

If the subject is a Roll-In subject (as defined in *Section 19.1 Roll-In Subjects*), then the second three (3) digit code begins with an R to designate the subject as a Roll-In. The R is followed by a sequential two digit number for that site. Therefore, the first Roll-In subject enrolled at site 101 is 101-R01, the second is 101-R02, and so forth.

# 7.7 Sonendo GentleWave System Treatment

After a subject has been enrolled in the study, the PI will begin the Sonendo GentleWave System treatment.

The Sonendo GentleWave System Treatment is defined as beginning when LuxaBite or a Tooth Cap is placed (start of placement) until 100% completion of the Sonendo GentleWave System. All other procedures will be categorized as traditional RCT procedures.

# 7.7.1 Sonendo GentleWave System Treatment Process

Use the Manufacturer's Operator's Manual and IFU for the treatment process.

To ensure optimal performance of the Sonendo GentleWave System, please ensure that the following has occurred prior to start of the Sonendo GentleWave System:

- Ensure that the occlusal platform is placed and formed correctly.
- Ensure that the cotton pellet is removed from the pulp chamber.
- Utlize Depth Gauge to size Sealing Cap for pulp chamber.
- If Sealing Cap size is incorrect, change the size. It is recommended to choose the next smaller Depth Gauge (larger Sealing Cap).
- Ensure that the guide tube is placed in the center of the pulp chamber.

If the sealing cap and/or handpiece must be changed during the treatment, a new handpiece should be obtained. Once the new handpiece has been attached according to the IFU, the treatment should recommence where it was stopped and treatment should continue.

# 7.7.2 Leakage

If fluid or air leaks in and/or out of the Sealing Cap and/or the subject tooth, stop the Sonendo GentleWave treatment and determine the cause. Leakage may be caused by:

- Presence of caries
- Fracture
- Break in the build-up or leakage from LuxaBite or Tooth Cap

*Note: There are certain circumstances that will require build-up to be removed and then replaced in order to perform a successful treatment after a leak* 

- Hand position of the PI
- Other items such as an issue with the irrigants

To avoid leakage, the following precautions should be taken:

- Do not tilt rock, rotate or move the handpiece.
- If the PI needs to adjust their hand or position, or if the patient wants to move, the treatment should be paused prior to movement.

Once a leak has been corrected, restart the Sonendo GentleWave System treatment. Treatment will commence from the point where it was stopped (exception: during leak test).

## 7.8 Control of Bleeding

Bleeding and control of bleeding during any RCT is expected and is considered standard of care. Bleeding is typically controlled through a combination of paper point usage, waiting for the bleeding to stop, starting the cone fit process and usage of intra-canal medications. If bleeding cannot be controlled and prevents the System from treating the tooth, the PI should pack the tooth with calcium hydroxide (Ca(OH)2) and restore the tooth with temporary material until the patient can be scheduled for a Second Procedure Visit according to standard of care.

## 7.9 Second Procedure Visit

The Sonendo GentleWave treatment may be completed on a subsequent visit, a Second Procedure Visit. The Second Procedure Visit can be scheduled according to standard of care.

At this visit, the PI should remove the  $Ca(OH)_2$  with the Sonendo GentleWave System. Use of files or irrigation to remove  $Ca(OH)_2$  is not allowed for the study.

## 7.10 Inability to Complete Treatment

If, for any reason, Sonendo GentleWave treatment cannot be completed over the course of no more than two visits, the subject will be considered as a Treatment Incomplete Subject. Subjects in the Treatment Incomplete Cohort will be documented as such but will not be followed for the study. No additional data will be collected on the Treatment Incomplete Cohort. Reasons for incomplete treatment may include, but are not limited to, periodontal issues, uncontrolled bleeding, root fracture, patient reported pain, etc.

These subjects will be counseled by the PI on any treatment they require. Subjects in the Treatment Incomplete Cohort will be responsible for any standard of care treatment.

## 7.11 Obturation

After the Sonendo GentleWave System treatment is completed; obturation, and coronal seal are required according to standard endodontic practices.

- 1. Dry the pulp chamber and the root canals in preparation for obturation.
- 2. Obturate the subject tooth using standard endodontic techniques. A warm vertical compaction method should be utilized as the obturation technique for this study.
- 3. A cone fit radiograph is recommended prior to completion of obturation.
- 4. Complete obturation to the full working length leaving the coronal 1-2mm for

extension of the restorative materials of each canal is recommended.

### 7.12 Coronal Seal

- 1. It is recommended to use a cotton ball dipped in alcohol to wipe the pulpal chamber floor and prepare for coronal seal and build-up.
- 2. Seal the pulp chamber floor and canal orifices with using a permanent restorative material (approx. 3mm thick), according to standard of care.
- 3. Complete the case according to standard endodontic procedure.

## 7.13 Intra-Procedure Assessments and Evaluations

The following information, among others, will be collected during traditional root canal therapy and the Sonendo GentleWave Treatment.

- 1. Procedure Time: Defined for this protocol as the time from dental dam placement until dental dam removal.
- 2. Procedural Details: Working Length, Master Apical File size, Irrigation, Calcification Assessment, additional therapies or procedures utilized and Material Utilization.
- 3. Enrollment Time: Study Enrollment time is equivalent to Sonendo GentleWave System Treatment Start Time.
- 4. Sonendo GentleWave Treatment Start Time: Defined for this protocol as starting when the LuxaBite or Tooth Cap is placed (start of placement) on the subject tooth.
- 5. Traditional Root Canal Therapy devices and instruments utilized.
- 6. Sonendo GentleWave System devices utilized.
- 7. Sonendo GentleWave Treatment End Time: Defined for this protocol as when the Sonendo GentleWave System user interface screen indicates 100% completion.
  - a. If the subject is required to return for a Second Procedure Visit, then the Sonendo GentleWave Treatment End Time for the first visit is defined as the time when the Investigator determines the subject tooth needs to be packed with calcium hydroxide.
  - b. Sonendo GentleWave Treatment End Time for the First visit: Defined for this protocol as the last time when Sonendo GentleWave Treatment is stopped.
- 8. Medications: Any antibiotics, analgesics and/or anti-inflammatory medications provided intra-procedure by the PI will be collected for the study and will be documented on the Concomitant Medication Log.
- 9. Radiographic Assessment: Working Length and Cone Fit radiographs, if applicable.
- 10. Adverse Events (SEE SECTION 10.0 Adverse Event)

## 7.14 Post Procedure Assessments and Evaluations

The following information will be collected post procedure;

- Diagnostic Radiographic Analysis: Periapical (PA) Parallel Radiograph, showing the periapical region surrounding the subject tooth should be collected for each visit. Additional radiographs completed as necessary by the PI will be collected for the study.
- 2. Cone Beam Computed Tomography (CBCT) radiograph post procedure is recommended.
- 3. Radiographic Evaluation of Obturation:
  - a. The PI will evaluate the radiographs to determine the level of obturation.
    - i. Short Fill: Sealer or obturation material <2mm above the apex.
    - ii. Flush Fill: Sealer or obturation material within 2mm of the apex.
    - iii. Overfill: Sealer or obturation material >2mm below the apex.
    - iv. Presence and size of sealer puff
- 4. AAE Case Difficulty Assessment: This form will be utilized by the PI after every Procedure Visit to assign a level of difficulty to a particular case.
- 5. Gracely Descriptor Differential Scale
- 6. Patient Satisfaction Survey: This is a questionnaire that asks the patient to rate their experience of the root canal procedure they had and compare it with their previous root canal procedure experience, if applicable. The questionnaire also asks the patient to indicate any sensations or pain felt during the procedure.

If the PI prescribes any antibiotics, analgesics and/or anti-inflammatory medications post procedure; these medications will be documented at subject's next study visit if the medications were taken by the subject. If the prescribed medications were not taken by the subject, the clinical site designee should make a note of this on the source document.

All subjects are instructed to contact the PI and/or clinical site designee in case of increased pain or discomfort after the procedure. If during the wait period between the Procedure Visit and next study visit, the subject has increased pain or discomfort, the PI will provide the subject with standard post-operative care and guidance.

All redacted source documentation with PI signature should be provided to the Sponsor for filing after each study visit. If changes are made to the source documents after PI signature, the updated source documents should be provided to the Sponsor for filing.

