	
 
Endodontic Assessments including Periradicular Tests (Percussion and Palpation), Cold Test, Root Resorption, Pulp Diagnosis, and Periradicular Diagnosis
 

	
 
Procedural details including Calcification Assessment, Irrigation, and Material Utilization
 

	Sonendo GentleWave System Devices Utilized
	Traditional Root Canal Therapy Devices and Instruments Utilized
	Procedure Time (dental dam placement to removal)
	Sonendo GentleWave Treatment Time (Treatment Time)
	Cone Beam Computed Tomography (CBCT) Sub-Set Evaluation
	Radiographic Evaluation of Obturation
	Adverse Events
Questionnaires	The following questionnaires will be completed for the study:
Completed for the Study	
 
McGill Short Form Pain Questionnaire at Baseline, 1, 2, 3, 7 and 14 days post-procedure, at all Follow-up Visits and at Unscheduled Visits, as necessary
 

•	Gracely Descriptor Differential Scale (DDS) at Baseline, immediately post procedure and 1 day post procedure
•	Patient Satisfaction Survey immediately post procedure
•	AAE Case Difficulty Assessment post procedure

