## 2.3 Healing Rates for Traditional Root Canal Therapy

While the literature presents many different definitions of healing, any future endodontic clinical studies should utilize a healing endpoint based upon both clinical and radiographic findings. The radiographic finding should be based upon the periapical index score, with PAI 1 or 2 indicating success. Additionally, no clinical signs or symptoms should be present. Separating complete healing and incomplete healing will also more clearly present study results.

Success rates over time varied widely across the literature. Generally, most healing had occurred 1 year following root canal treatment, though healing was shown to take up to 4 years or more. Thus, success rates should also be presented at each time-point studied and not just a cumulative number over a range of follow-up periods. An approximate success rate for 1 year follow-up would be 68-70% while that success rate would increase to 80-85% after four years.

While effective chemomechanical canal preparation is extremely important, the literature indicated other factors significantly affected long-term prognosis for the patient. If a patient presented with apical periodontitis and had a periapical lesion, the long-term success was significantly lower. Thus, including a large number of patients with a pre-operative periapical radiolucency could result in lower long-term success rates. Effective obturation to within 2 mm within the radiographic apex and effective coronal restorations also improved long-term success. The number of roots treated and mid-treatment complications could also impact success rates. These facts highlight the importance of choosing the appropriate patient

population and standardizing the treatment regimen in clinical studies so that the variable being studied can be reliably assessed.

While a number of studies have been published regarding the healing and success rates following root canal treatment, the quality of this literature is generally less than other medical disciplines. A dearth of randomized, controlled trials exists in endodontic research, and a large number of retrospective studies are published. Finally, the lack of standardization of study design and clinical endpoints across studies makes the comparison of results between studies difficult at best. *(See Appendix I. Healing Literature Report)* 

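### The obturation grades in Section 7.14 overlap for fills less than 2 mm short of the apex and leave fills more than 2 mm short with no grade

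*Combined protocol and SAP*

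**What the plan says.** Section 7.14, item 3, sets the grading rule and names the rater: "The PI will evaluate the radiographs to determine the level of obturation". It gives three grades:

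- "Short Fill: Sealer or obturation material <2mm above the apex"
- "Flush Fill: Sealer or obturation material within 2mm of the apex"
- "Overfill: Sealer or obturation material >2mm below the apex"

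The presence and size of any sealer puff are recorded separately. The item cites a published source for the evaluation. No other section restates or corrects the cut-offs.

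The synopsis (Section 1.0) lists "Radiographic Evaluation of Obturation" among the assessments collected for the study. Section 13.0 says that qualitative variables in general will be summarised by the number and percentage of patients in each category.

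The background gives the 2 mm distance a meaning of its own. Section 2.3, reviewing prognostic factors, states: "Effective obturation to within 2 mm within the radiographic apex and effective coronal restorations also improved long-term success".

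**The concern.** A categorical item can be tabulated only if every case fits one category and no case fits two. The printed cut-offs fail both conditions on the side of the apex where a short filling ends.

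The overlap lies in an ordinary range. Section 7.11 recommends filling to the full working length, and Section 2.2.5 describes a working length that looks accurate as one ending 0 to 2 mm short of the apex on the radiograph. Taken together, a filling placed as recommended could well end where two grades apply.

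The labels also sit badly with Section 2.3. A filling that section regards as favourable may be recorded as Short, while a filling that falls outside the favourable range on the short side has no code. The investigator assigns the grade, at up to 8 sites. Unlike the periapical index, which goes to blinded independent reviewers (Section 7.4.4), no central reading is described that would expose different conventions between sites. At stake is whether the obturation table describes the fillings correctly, in a single-arm study that sets its healing rate beside published rates.

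**Working it through.** The plan gives no figure to reproduce here, so the check is to apply the definitions as printed.

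**Inputs (all from Section 7.14, item 3).** Let d be the signed distance in mm from the apex to the end of the filling, positive when the filling stops short of the apex and negative when it passes beyond it. Overfill is defined as below the apex, so above the apex must mean short of it.

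- Short Fill: 0 < d < 2
- Overfill: d < −2
- Flush Fill depends on how within 2 mm is read: (A) two-sided and inclusive, |d| ≤ 2; (B) two-sided and strict, |d| < 2; (C) short side only, 0 ≤ d ≤ 2.

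**Result of applying the rule:**

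| d (mm) | Reading A | Reading B | Reading C |
|---|---|---|---|
| +4, +3, +2.5, +2.01 | none | none | none |
| +2 | Flush | none | Flush |
| +1.99, +1.5, +1, +0.5 | Short and Flush | Short and Flush | Short and Flush |
| 0 | Flush | Flush | Flush |
| −0.5, −1 | Flush | Flush | none |
| −2 | Flush | none | none |
| −2.01, −3 | Overfill | Overfill | Overfill |

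**What follows:**

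1. The interval 0 < d < 2 is contained in Flush Fill under A, B and C. Every filling that meets Short Fill also meets Flush Fill.
2. Every d > 2 fails all three definitions under A, B and C. A true underfill has no code.
3. A filling exactly at the apex (d = 0) is Flush only, so the overlap excludes that point.
4. Whether d = +2 and d = −2 have a grade depends on whether within includes the boundary. Whether fillings up to 2 mm beyond the apex have a grade depends on whether Flush is two-sided.

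**Would reversing one inequality sign be enough?** Suppose Short Fill were d > 2.

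- Under A, every value in the table falls in exactly one grade.
- Under B, d = +2 and d = −2 have no grade.
- Under C, fillings beyond the apex by up to and including 2 mm have no grade.

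A change of sign therefore repairs the scheme only if Flush Fill is also declared two-sided and inclusive.

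**The case against.** The strongest case against is that nothing planned rests on this variable, and that is correct. Obturation level is not part of the primary effectiveness endpoint (Section 3.1), the primary safety endpoint (3.2) or the twelve secondary endpoints (3.3). Section 13 names no covariate, subgroup, population or test that uses it. Extrusion of filling material has its own definition in Section 10.10, based on gross overextension with symptoms, so the safety endpoint does not depend on these grades either.

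A reader might infer that adequate fillings will be recorded as Short and that the data will come out reversed. The text does not support this. A filling 1 mm short meets both definitions, so following the rule exactly permits Short but does not force it. Investigators are trained in the obturation protocol (Section 19.0), and many may recognise a slipped inequality sign, because the label and the mirrored Overfill cut-off both point that way. The documents do not show how sites actually coded.

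A reader might also infer that the comparison with the literature depends on this grade. Section 2.3 names fill level as one of several prognostic factors and stresses patient selection and a standardised treatment regimen. It plans no adjustment or comparison by fill level.

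Two cautions stand. The CRF and the cited source are not available here, so the intended wording cannot be confirmed. The text was also machine-read, so a misread sign cannot be wholly excluded, although the opposite sign in the Overfill line came through sensibly. None of this removes the overlap or the gap in the printed rule.

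**Conclusion.** The three grades in Section 7.14 are neither exclusive nor exhaustive. Every filling ending more than 0 and less than 2 mm short of the apex meets two grades, and every filling ending more than 2 mm short meets none. This holds under all three readings of within 2 mm, and it assumes only that above the apex means short of it, which the Overfill definition requires. The Short label also conflicts with Section 2.3.

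The consequence is small. It reaches the recorded obturation level, its tabulation under the general rule of Section 13.0, and any descriptive use of it when healing is set beside the literature. It does not reach the primary analysis, the safety analysis, the sample size or any listed endpoint. The share of fillings affected cannot be worked out from the documents. Because post-procedure periapical films are collected for the study (Sections 7.14 and 8.0), the grade can be recovered by re-reading. This is a minor drafting error worth correcting.

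**What to change.** Reconcile the three definitions in Section 7.14 around the 2 mm boundary already used, so that each filling has exactly one grade and Short Fill begins where Flush Fill ends. State whether exactly 2 mm counts as Flush, and whether Flush covers both sides of the apex or only the short side. If only the short side, give fillings up to 2 mm beyond the apex a grade. Check the wording against the cited source and the original PDF, and make the CRF match. Then re-read the post-procedure films already coded, using the corrected definitions.

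This corrects a recording rule and changes no treatment. The cost is a few words in Section 7.14, a CRF check and a recheck of films on file, which at a maximum enrolment of 120 is the post-procedure films of no more than 120 subjects.

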# 7.15 Out-Patient Questionnaires

# 7.15.1 McGill Short Form Pain Questionnaire

Subjects will be asked to complete a McGill Short Form Pain Questionnaire for their physical mouth and tooth pain at 1, 2, 3, 7 and 14 days post-procedure and at all Follow-up Visits . This

form should be completed and returned to the clinical site designee at the next study visit or using certified mail or using a pre-paid FedEx envelope.

If the subject is unable to complete one or more outpatient McGill Short Form Pain Questionnaire(s) then the clinical site designee may call the subject and complete the questionnaire(s) themselves based upon responses provided by the subject.

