#### **3.3 Secondary Endpoints**

The following outcomes will be assessed:

- 1. McGill Short Form Pain Questionnaire
- 2. Gracely Descriptor Differential Scale (DDS) 59
- 3. Patient Satisfaction Survey
- 4. AAE Case Difficulty Assessment
- 5. Soft Tissue Lesions
- 6. Swelling
- 7. Root Canal Therapy Retreatment
- 8. Treatment Time
- 9. Procedure Time
- 10. Periapical Index (PAI) analyzed utilizing radiographic analysis by independent reviewer
- 11. Cone Beam Computed Tomography (CBCT) Sub-Set Evaluation
- 12. Additional Radiographic Analysis may be completed

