#### 5.2 Pre-Procedure Exclusion Criteria

- 1. Poor oral hygiene according to a Poor, Fair, Good Scale
- 2. Subject tooth with  $\geq$  Class II Mobility
- 3. Subject tooth with Periodontal Pocket Depth  $\geq 6$
- 4. Periodontal probe reaches the apex of the subject tooth
- 5. Furcation involvement originating from periodontal disease, on the subject tooth, one and/or two adjacent teeth in direct contact with the subject tooth
- 6. Subject tooth with  $\geq$  Class III endodontic furcation involvement
- 7. Subject tooth with open or incompletely formed root apices
- 8. Vertical fracture, horizontal fracture, or perforation extending below the Cemento-Enamel Junction (CEJ) of the subject tooth
- 9. Caries or another condition of the subject tooth that
  - a. prevents adequate seal of the device
  - b. requires a separate procedure for crown lengthening
  - c. requires a post

- d. provides inadequate biological width for crown retention
- 10. Any dental treatment on the subject tooth completed with the known use of devitalizers or formocresol
- 11. Subject tooth having previous or attempted pulpectomy or root canal therapy
- 12. One or two adjacent teeth in direct contact with the subject tooth requiring root canal therapy, pulpectomy or pulpotomy
- 13. Any tooth on the same side of the oral cavity as the subject tooth with a source of pain
- 14. Extraoral swelling on or around the subject tooth that has not undergone antibiotic treatment or a procedure to treat the swelling prior to RCT
- 15. Any condition that would preclude tolerance of a root canal therapy including but not limited to being in a reclined and prolonged position in a dental chair, use of a dental dam, or ability to have an open mouth for extended periods of time (>15 minutes) (e.g. history of seizure within the last 5 years, severe asthma, or extreme gag reflex)
- 16. Any other condition that the Investigator determines is unacceptable for enrollment into the study
- 17. Nonodontogenic facial pain
- 18. History of cancer within the oro-maxillofacial region
- 19. History of any cancer within the last two years, including skin cancer
- 20. History of head and/or neck radiation therapy
- 21. Immunocompromised patients (i.e. corticosteroid usage)
- 22. Any medical history that affects blood coagulation (e.g. bleeding disorders)

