# 7.15.2 Gracely Descriptor Differential Scale (DDS)

Subjects will be asked to complete a Gracely Descriptor Differential Scale Questionnaire wherein they will be asked to rate the sensation felt in the tooth treated with Sonendo GentleWave System at 1 day post-procedure. This form should be completed and returned to the clinical site designee at the next study visit or using certified mail or using a pre-paid FedEx envelope.

If the subject is unable to complete the outpatient Gracely Descriptor Differential Scale Questionnaire then the clinical site designee may call the subject and complete the questionnaire themselves based upon responses provided by the subject.

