    - i. Probing Pocket Depth: The distance between the height of the free gingival margin and the height of attachment apparatuses below (bone, cementum, and periodontal ligament). Using a calibrated periodontal probe, the periodontal pocket depth should be recorded on the mesial, middle, and distal aspects of both the buccal and lingual sides of the tooth
    - ii. Mobility

- None: No distinguishable sign of movement.
- Class I: The first distinguishable sign of movement greater than normal.
- Class II: Horizontal tooth movement no greater than 1 mm.
- Class III: Horizontal tooth movement greater than 1 mm, with or without the visualization of rotation or vertical depressability.
- Any mobility other than none should be considered abnormal.
- iii. Swelling: This assessment includes the type and location of swelling.
- iv. Soft Tissue Lesions: This assessment includes the lesion presence, color and size where applicable. This assessment shall also include ulcerations and fistula/sinus tract.
- v. Root Resorption
- vi. Furcation Involvement/Furcation Defect
  - Class I: The furcation can be probed, but not to a significant depth.
  - Class II: The furcation can be entered into but cannot be probed completely through to the opposite side.
  - Class III: The furcation can be probed completely through and through.
  - Class IV: The furcation can be probed through and through, and recession reveals a visible furcation.
- 7. Endodontic Assessments including:
  - a. Periradicular Tests (Percussion and Palpation)
    - None (-): No discomfort at all.
    - Mild (+): Little discomfort, but may be noticeable by the patient.
    - Moderate (++): Some noticeable discomfort.
    - Severe (+++): Definitive discomfort.
  - b. Periradicular Diagnosis:
    - Normal Apical Tissue: Teeth with normal periradicular tissues that are not sensitive to percussion or palpation testing. The lamina dura surrounding the root is intact, and the periodontal ligament space is uniform.
    - Symptomatic Apical Periodontitis: Inflammation, usually of the apical periodontium, producing clinical symptoms including a painful response to biting and/or percussion or palpation. It might or might not be associated with an apical radiolucent area.
    - Asymptomatic Apical Periodontitis: Inflammation and destruction of apical periodontium that is of pulpal origin, appears as an apical radiolucent area, and does not produce clinical symptoms.

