## 7.19 Mail, Telephone and Dentist Contact

If the subject is unable or unwilling to attend all study visits, the subject consents to be called or sent mail by the PI or clinical site designee to provide information about their dental status.

The data provided via telephone contact or mail may include the following:

- 1. Medical and Dental History and Exam
- 2. Medication Regime
- 3. McGill Short Form and/or Numeric Rating Scale

The clinical site designee will follow the Numeric Rating Scale mentioned below or verbally ask questions on the McGill Short Form Pain Questionnaire. When asking the patient to rate their pain per the Numeric Rating Scale, the following question should be asked:

"On a scale of 0 to 10, with 0 being 'no pain' and 10 being the 'most intense pain imaginable', what would you rate the severity of your tooth pain right now"?

4. Adverse Events

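### After day 1 the only scheduled pain questionnaire is not tied to the treated tooth, so study-tooth pain cannot be separated from other mouth pain.

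*Combined protocol and SAP*

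**What the plan says.** Three pain questions differ in what they ask about.

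- **McGill, section 7.15.1** (days 1, 2, 3, 7 and 14, and all follow-up visits): "Subjects will be asked to complete a McGill Short Form Pain Questionnaire for their physical mouth and tooth pain".
- **Gracely scale, section 7.15.2** (the day 1 out-patient form): subjects are to "rate the sensation felt in the tooth treated with Sonendo GentleWave System".
- **Telephone numeric scale, section 7.19**: "what would you rate the severity of your tooth pain right now". This route applies "If the subject is unable or unwilling to attend all study visits".

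Section 3.3 introduces twelve secondary endpoints with "The following outcomes will be assessed". The McGill is listed first, but the list is not ranked. Section 3.0 names post-procedure pain, compared with a literature control, as part of the purpose.

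At entry, exclusion 13 in section 5.2 reads "Any tooth on the same side of the oral cavity as the subject tooth with a source of pain". Section 7.1 asks for such teeth to be treated before screening.

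Section 3.1 defines the primary endpoint for the subject tooth. It uses PAI together with the absence or reduction of signs and symptoms, without saying which assessments supply them.

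**The concern.** The Gracely wording shows that the plan can tie a pain question to the treated tooth. The McGill, which carries the pain record for the remaining 24 months, is not tied in this way. A subject with a sound study tooth and a painful tooth on the other side would, on the wording of section 7.15.1, report that pain on the study form.

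The comparison is with published data, so no concurrent arm carries the same background of mouth pain and lets it cancel. Section 13 has no rule for separating pain by site: section 13.5 states only when the secondary analysis takes place. A McGill summary at month 12 or 24 would mix the treated tooth with the rest of the mouth, and the mixture could not be undone afterwards.

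**Working it through.** **1. Coverage, from section 8.0 (Schedule of Visits).**

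| Time point | McGill | Gracely |
|---|---|---|
| Baseline | yes | yes |
| Immediately post-operative | no | yes |
| Day 1 | yes | yes |
| Days 2, 3, 7, 14 | yes | no |
| Months 6, 12, 18, 24 | yes | no |

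Post-procedure McGill time points: 1 + 4 + 4 = 9. A tooth-specific scale accompanies one of them (day 1), which leaves 9 − 1 = 8 without one.

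**2. What the entry safeguards cover.** Exclusion 13 and the treatment before screening both concern the same side of the mouth. Section 5.2 also excludes adjacent teeth needing root canal therapy, nonodontogenic facial pain, chronic-pain conditions and long-term analgesic use. Two sources remain: an opposite-side painful tooth at entry, and any tooth that becomes painful during 24 months. Section 7.4.4 gives no stem for the Baseline McGill, so opposite-side pain in the Baseline score is possible but not shown.

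**3. Does any rule carry these scores into the primary endpoint?** None was found. Section 3.1 is at tooth level, and the McGill is listed separately in section 3.3. Section 7.17.2 collects subject-tooth swelling and soft-tissue lesions, percussion and palpation, and a periradicular diagnosis that distinguishes symptomatic from asymptomatic disease. What remains is a gap: section 3.1 does not say which of these fields count, and does not rule the questionnaires out.

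**4. The same gap with mobility.** Section 7.17.2 notes: "Any mobility other than none should be considered abnormal". Section 5.2 excludes Class II mobility and above, so a Class I tooth can enter with a finding labelled abnormal. Section 3.1 does not say whether that is a clinical sign for the endpoint.

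**5. The plan's own figure (section 13.1).** Exact binomial, n = 86, null 0.70, 2.5% per tail: reject at 69 or more successes (upper-tail probability 0.022) or at 51 or fewer. Power at 0.85 is 0.914, against the stated figure of about 90%. Enrolment: 108 × 0.80 = 86.4. The plan's arithmetic reproduces, and the wording problem does not change it.

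**6. A what-if, not an estimate.** Suppose that mouth-level pain were used to score the primary endpoint, and that a share f of true successes was lost for that reason alone. The observed rate would be 0.85 × (1 − f).

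| f (assumed) | Observed rate | Exact power |
|---|---|---|
| 0 | 0.850 | 91.4% |
| 2% | 0.833 | 82.0% |
| 5% | 0.8075 | 61.2% |
| 10% | 0.765 | 24.9% |

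The documents give no value for f and do not prescribe this use of the scores. The calculation runs in one direction only and lets no tooth count as healing instead. It shows only why section 3.1 should close the gap.

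**The case against.** The strongest reply is that this is a wording matter in one of twelve unranked secondary outcomes. The primary endpoint is at tooth level, and the examination supplies tooth-level symptoms at each visit. The telephone scale is a fallback, is not a listed endpoint, and yields no radiograph, so it cannot by itself establish that a tooth is healed. The printed McGill form is not in the supplied text, and its stem may name the tooth. A mouth-wide question also has merit: section 7.4.4 lists referred pain as a descriptor of pulpitis, and soft-tissue pain from the procedure belongs to post-procedure pain.

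Most of this stands. It limits the point to the pain results and argues against replacing the stem. It does not answer the point itself: followed as written, section 7.15.1 yields a score whose source is unknown at eight time points.

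A reader might go further and infer that several of the 86 teeth would be misclassified on the primary endpoint. With an assumed 2% to 10% of subjects having other mouth pain at month 24, 86 × 0.02 = 1.7 and 86 × 0.10 = 8.6 teeth, against a margin of 73.1 − 69 = 4.1 between expected successes (86 × 0.85) and the pass mark. The documents do not support that reading. The rate is assumed. Other-tooth pain cannot turn a failure into a failure, so the base is the 73.1 expected successes (1.5 to 7.3 teeth). A tooth with reduced radiolucency or reduced Baseline symptoms still counts as healing. Relief of unrelated pain could also move a tooth the other way.

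**Conclusion.** The point holds for the pain results. From day 2 to month 24 the scheduled pain questionnaire cannot distinguish the study tooth from the rest of the mouth, and the telephone scale does not identify the tooth either. The entry safeguards reduce this but do not remove it. It matters because pain is part of the stated purpose and there is no concurrent control. The conclusion assumes that the form follows the scope in section 7.15.1.

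It does not follow that mouth pain, telephone ratings or mobility enter the primary endpoint. Such use is left open by the silence of section 3.1 and is not a stated rule. No number of misclassified teeth can be derived, and no change to the sample size follows. Nor is the McGill the lead pain endpoint, although its place at the head of the list might suggest it.

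**What to change.** 1. **McGill form and telephone script.** Keep the present McGill stem for continuity. Add one item asking whether the pain is in the study tooth (tooth number given), elsewhere in the mouth, or both.
2. **Analysis.** Report study-tooth pain and other mouth pain separately beside the total score. Fix in advance how answers of both are shown, because one score cannot be divided.
3. **Section 3.1.** State that signs and symptoms are those of the subject tooth, and name the fields already collected that supply them. The sponsor should reconcile this section with the mobility note in section 7.17.2 and say whether mobility, pocket depth and furcation count. That is a clinical decision, and section 5.2 itself distinguishes endodontic from periodontal furcation involvement.

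**Cost.** One item on the form and in the script, a short addition to section 3.1, and one more table. Enrolment was expected from August 2014 and this revision is dated March 2015, so some forms may already be complete without the item. Form version must be recorded and those data shown separately. Replacing the stem would cost more, because it would break comparison within subjects who began on the old wording. Location is self-reported, so referred pain may still be placed wrongly.
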